## 7.9.3 Analysis of Other Efficacy Endpoints

The PGIC score will be analyzed with ANOVA model at Weeks 4 and 12. (Table 14.2.8.1)

The response rate based on PGIC score (i.e. either 6 or 7) will be analyzed with logistic regression at Weeks 4 and 12. (Table 14.2.8.2)

The change from baseline to Weeks 4 and 12 in PSQI total and each domain score will be analyzed with ANCOVA model. The analysis model will include baseline value as a covariate and treatment as fixed effect. (Table 14.2.9.1) In addition, PSQI total score in categories will be summarized for each visit (Table 14.2.9.2). The following categories will be used for the analysis;

- Good sleep quality: PSQI total score  $\leq 5$

- Poor sleep quality: PSQI total score > 5

The ANCOVA model will be applied to analyze the change from baseline to Weeks 4 and 12 in total and each domain score of the MENQOL. The analysis model will include baseline value as a covariate and treatment as fixed effect. (Table 14.2.10)

The change from baseline to Weeks 4 and 12 in each domain i.e. Physical Functioning, Role Physical, Bodily Pain, General Health, Vitality, Social Functioning, Role Emotional, Mental Health, Physical Component Summary [PCS], and Mental Component Summary [MCS]) score of the SF-36 will be analyzed using ANCOVA model with treatment as fixed effects and baseline value as covariate. (Table 14.2.11)

The ANCOVA model will be applied to analyze the change from baseline in the average daily severity score of moderate to severe VMS at Weeks 4 and 12, defined as  $2xFmo + 3xFse$ . The analysis model will include baseline value as a covariate and treatment as fixed effect. (Table 14.2.12)

#### 7.9.4 Sensitivity Analysis of Efficacy Endpoints

Sensitivity analyses for Efficacy Endpoints as following.

The sensitivity analysis will be conducted using primary analysis model with applicable covariates for ITT subjects without using antidepressants. (Table 14.2.2.1.A, Table 14.2.2.1.B, Table 14.2.2.2.A, Table 14.2.2.2.B)

The primary endpoints will also be analyzed using an ANCOVA model at week 4 and 12. The analysis model will include baseline value of the endpoint as a covariate and treatment as fixed effect. (Table 14.2.3.1, Table 14.2.3.2)

### 7.10 Safety Assessments

The safety evaluation will be purely descriptive using descriptive statistics (N, mean, SD, median minimum and maximum) or frequency tables where appropriate using SAF population, unless otherwise specified. No imputation will be made in case of missing values.

#### 7.10.1 Adverse Events

The frequency and incidence of TEAEs will be summarized by System Organ Class (SOC) and Preferred Term (PT) by treatment and overall. The SOC is sorted by International order; then within SOC, PT is sorted by descending counts under MT-8554 Total column, then descending counts under placebo column, then alphabetic order for PTs with the same count.

Following summaries will be presented:

- Overall summary of TEAE (Table 14.3.1.1)

- TEAEs by SOC and PT (Table 14.3.1.2)
- TEAEs by SOC, PT and time of onset (Table 14.3.1.3)
- TEAEs by SOC, PT and severity (Table 14.3.1.4)
- TEAEs leading to discontinuation of study medication by SOC and PT (Table 14.3.1.5)
- Serious TEAEs by SOC and PT (Table 14.3.1.6)
- TEAEs by SOC, PT and drug relationship (Table 14.3.1.7)
- [REDACTED]
- Adverse reactions by SOC and PT (Table 14.3.1.9)
- Serious Treatment Adverse reactions by SOC, PT (Table 14.3.1.10)
- TEAEs by SOC and PT for AEs with frequency  $\geq 3\%$  (or 5%) in total MT-8554 group (Table 14.3.1.11)
- [REDACTED]

For each of the summaries will be done at the subject level - multiple occurrences of the same event within a subject will be counted once in the summaries by SOC and PT; multiple occurrences of the same event within a subject will be counted once in the maximum intensity category (severe > moderate > mild) and/or maximum drug relationship category (reasonable possibility, no reasonable possibility) and/or the earliest occurrence. If intensity or relationship is found to be missing the most severe occurrence will be imputed for that particular summary.

All AEs for each subject, including multiple occurrences of the same event, will be presented in full in a comprehensive listing including subject number, treatment, severity, seriousness, action taken, outcome, relationship to treatment, onset/stop date and duration.

Deaths that occur during the study will be listed in a data listing. The data listings for serious TEAE and TEAE leading to discontinuation will be generated as well.

[REDACTED]

### 7.10.2 Laboratory Tests

For all continuous laboratory parameters, the lab values and change from baseline to post baseline visits are summarized by treatment group and visit.

For all discrete laboratory parameters, the lab values are summarized with count and percentage by treatment group and visit. (Table 14.3.2.1, Table 14.3.2.2, Table 14.3.2.3, Table 14.3.2.4, Table 14.3.2.5)

The lab tables will be generated for each Lab categories (Hematology, Coagulation, Biochemistry and Hormones and Urinalysis).

All laboratory data will be listed with clinically relevant values flagged (L=Lower than lower limit of normal range or H=Higher than upper limit of normal range).

In addition, following clinical relevant ranges (and flags) will also be considered for summary table. The count and percent of subjects meeting the criteria will be presented. (Table 14.3.2.6)

- ALT  $\geq 3 \times$  Upper Limit of Normal Range (ULN), 5 $\times$  ULN, 8 $\times$  ULN, 10 $\times$  ULN
- AST and/or ALT  $\geq 3 \times$  ULN, 5 $\times$  ULN, 8 $\times$  ULN, 10 $\times$  ULN
- AST and/or ALT  $\geq 3 \times$  ULN with Total bilirubin  $\geq 2 \times$  ULN
- Total bilirubin  $\geq 2 \times$  ULN
- Creatinine  $\geq 2 \times$  ULN

### **7.10.3 Vital Signs**

Vital signs data will be summarized descriptively in tables by treatment and scheduled visit. (Table 14.3.3.1) All vital sign data will be listed.

### **7.10.4 ECGs**

ECG parameter values and changes from baseline will be summarized descriptively by treatment and scheduled visit. (Table 14.3.3.2.1)

For ECGs, number and percentage of subjects meeting the criteria listed below will be presented in tables (Table 14.3.3.2.2):

- QTc  $> 500$ ms
- QTc  $> 480$ ms
- QTc  $> 450$ ms
- Change from baseline in QTc  $> 30$  msec
- Change from baseline in QTc  $> 60$  msec

These criteria will be applied to both QTcB and QTcF.

Shift tables will present the changes in clinically relevant categories from baseline to EOT/Early discontinuation visit. The categories are; “QTcB  $\leq 450$ msec”, “QTcB  $> 450$  to  $\leq 480$ msec”, “QTcB  $> 480$  to  $\leq 500$ msec”, “QTcB  $> 500$ msec”. (Table 14.3.3.2.3)

Similar shift table will be also created for QTcF. The categories are; “QTcF  $\leq 450$ msec”, “QTcF  $> 450$  to  $\leq 480$ msec”, “QTcF  $> 480$  to  $\leq 500$ msec”, “QTcF  $> 500$ msec”. (Table 14.3.3.2.4)

All ECG parameters and findings will be listed.

### **7.10.5 Physical Examinations**

Physical examination data will be summarized descriptively in tables by treatment and visit (Table 14.3.4).

All physical examination data will be listed.

### 7.10.6 Breast Examination

The breast examination data will be summarized in tables by treatment and visit (Table 14.3.5). All breast examination data will be listed.

### 7.10.7 Endometrial Safety

#### 7.10.7.1 Endometrial Thickness Measured by Transvaginal Ultrasound (TVU)

The endometrial thickness as measured by TVU will be summarized in the tables by treatment and visit as below. (Table 14.3.6.1, Table 14.3.6.2)

1. Summary table presenting mean and SD for baseline, post baseline visits and change from baseline
2. Summary table of endometrial thickness by category (<5, 5 to 8, >8)
3. Summary table for category of change from baseline (>3 mm, >5 mm)

[figure not shown]
The central reading data will be used for the analysis.

#### 7.10.7.2 Endometrial Histology (Endometrial Biopsy)

The Endometrial biopsy data will be summarized in the tables by treatment and visit as below (Table 14.3.7.1, Table 14.3.7.2).

1. Summary tables of proportion of subjects in abnormal\* category
2. Shift table for change in abnormal category from baseline to week 12

\*Note: The histological categories are based on 2003 draft FDA guidance

The data from adjudication committee will be used for the analysis.

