4.5.2 Discontinuation from study

Subjects may withdraw from the study for any reason. The Investigator will discontinue a subject from the study if ANY of the following criteria are met:

- The subject wishes to voluntarily withdrawal from the study
- The subject is lost to follow-up
- The subject who experiences elevated ALT or AST $>3 \times$ ULN and a total bilirubin $>2 \times$ ULN (such subjects should be treated per standard of care and followed till resolution.)
- The subject has an abnormal baseline endometrial biopsy result, as assessed by the endometrial biopsy adjudication committee.
- The subject has an abnormal result from an endometrial biopsy conducted at any time during the study based on Investigator's judgement (The biopsy report or slides may be requested for central assessment).
- The subject has endometrial thickness of ≥ 5 mm as measured by transvaginal ultrasound conducted at any time during the study based on Investigator's judgement (The images may be requested for central assessment).
- Continuing the subject in the study off treatment would be detrimental to the subject's safety in the opinion of the Investigator

If a subject is discontinued prematurely from the study, the date the subject is withdrawn from the study and the reason for withdrawal will be recorded on the eCRF.

In case of discontinuation from study, the EOT visit assessments should be performed, as far as possible (Sections 5.2.3.5 and 5.2.4) and any unresolved AEs or SAEs will be followed up according to Section 8.10.

The Investigator must make every effort to contact the subject to review all AEs. In the event that a subject drops out of the study at any time, the reason for discontinuation must be fully documented in the source documents and the eCRF. The Investigator site personnel will document the AEs and any other assessments in the source documents and will make every effort to complete all required EOS assessments.

Subjects withdrawn from the study following randomization may not re-enter the study.

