**Table 5 Derived Analysis Visit Windows**

	Nominal day	Window
Baseline	NA	NA
Day 1	Day 1 (First dose day)	NA
Week 2	Day 15	Day 7 to 21
Week 4	29	Day 22 to 42
Week 8	57	Day 43 to 70
Week 12	85	Day 71 to 98
Week 16 (FU)	115	NA

The analysis visits are derived according to the following criteria:

- The unscheduled visits are not used for the deriving.
- If a study visit is the only one in an analysis window, this study visit becomes the derived analysis visit.
- If there are multiple visits in a visit window, the closest visit to the nominal day becomes the analysis visit. In the event that two visits are the closest visits to the nominal day and equally distanced to the nominal day, the visit after the nominal day becomes the derived visit.
- The follow-up visit will not be derived. The study visit will be used.
- Unscheduled visits and retests (same visit number assigned), will not be displayed in by-visit summary tables, but will be included in the data listings. All data will be listed. Listings will include treatment, scheduled, unscheduled, retest and early discontinuation data.
- The screening and run-in visits are carried to derived visits
- The efficacy endpoints based on diary data use different windows. See Section 5.4.1.

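### Biopsies taken before Day 71 or at unscheduled visits are left out of the Week 12 endometrial shift table, so tabulated incidence of abnormal histology can be incomplete

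*SAP*

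**What the plan says.** Incidence of endometrial hyperplasia on biopsy is a safety endpoint (Protocol 2.2.5; SAP 2.4.8). For women with a uterus, the post-baseline biopsy and ultrasound are done at Week 12 or early termination (Protocol 5.2.3.5, 6.7.5, 6.7.6). Protocol Table 1 schedules none in between.

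SAP 7.10.7.2 plans two biopsy outputs, both from adjudication committee data. One is the proportion of women in the abnormal category; the other is a "Shift table for change in abnormal category from baseline to week 12". The section opens with "The Endometrial biopsy data will be summarized in the tables by treatment and visit as below".

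SAP 5.4.6 and Table 5 define visits by study day. A visit alone in its window takes that window's label: "If a study visit is the only one in an analysis window, this study visit becomes the derived analysis visit". Where several fall together, "If there are multiple visits in a visit window, the closest visit to the nominal day becomes the analysis visit". On unscheduled visits the rule is "The unscheduled visits are not used for the deriving"; they are also kept out of by-visit tables but are listed. Only diary-based efficacy endpoints have different windows.

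Protocol 4.5.2 includes among its reasons for discontinuation: "The subject has an abnormal result from an endometrial biopsy conducted at any time during the study". It has a parallel item for endometrial thickness of 5 mm or more. Both are qualified as resting on the Investigator's judgement.

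The ECG shift table in SAP 7.10.4 runs "from baseline to EOT/Early discontinuation visit".

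**The concern.** The protocol treats Week 12 and early termination as one visit (Visit 7, EOT). The SAP separates them by study day and then builds the shift table on Week 12 alone. A woman who leaves early and is biopsied on leaving has a post-baseline histology result, but that table has no place for it unless she left on Day 71 or later.

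This matters because an endometrial finding can itself be the reason for leaving, so the omission can be related to the outcome being counted. If abnormal histology is rare, one or two missing cases could change how an arm reads. The by-visit proportion table is not a full substitute. It spreads early biopsies over several visits, misses some altogether, and under SAP 5.3 uses by default a denominator of everyone in the treatment group, including women without a uterus. No overall incidence per arm is described.

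**Working it through.** The documents give no figure for this point that could be reproduced. The check applies the Table 5 rules to every possible early-termination day.

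**Inputs (SAP Table 5)**

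| Analysis visit | Window | Nominal day |
|---|---|---|
| Week 2 | Day 7–21 | 15 |
| Week 4 | Day 22–42 | 29 |
| Week 8 | Day 43–70 | 57 |
| Week 12 | Day 71–98 | 85 |

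Early termination is taken as any day from 1 to 84, that is, before the nominal Week 12 day.

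**Step 1. Shift table.** Days 71 to 84 fall in the Week 12 window: 84 − 70 = 14 days, and 14/84 = 17%. Days 1 to 70 do not: 70/84 = 83%. No EOT or last-value rule brings these biopsies back, and SAP 7.10 states that missing safety values are not imputed.

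**Step 2. By-visit proportion table.** Assume that the Week 2, 4 and 8 visits took place on their nominal days and that the closest-visit rule selects whole visits, as SAP 5.4.6 is worded. The 70 excluded days then split as follows.

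| Outcome | Days | Count |
|---|---|---|
| No window | 1–6 | 6 |
| Scheduled visit is closer, so the termination visit is not selected | 16–21, 30–42, 58–70 | 6 + 13 + 13 = 32 |
| Relabelled Week 2, 4 or 8 | 7–15, 22–29, 43–57 | 9 + 8 + 15 = 32 |

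Check: 6 + 32 + 32 = 70. Only the last group appears in the by-visit table.

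**Step 3. Sensitivity.** Moving the scheduled visits 3 days early or 3 days late (the protocol's visit window) gives 6 / 23 / 41 in both cases. If a programmer applied the closest-visit rule only to visits with a biopsy, no biopsy would be lost to a closer visit, and the split would be 6 / 0 / 64 (32 + 32 = 64). The 70 days outside the shift table are the same in every case.

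**Step 4. Unscheduled biopsies.** Protocol 5.2.7 defines a site visit outside the schedule for safety reasons as unscheduled. SAP 5.4.6 keeps such visits out of both derived visits and by-visit tables. A for-cause biopsy at such a visit is therefore in neither biopsy table, whatever its study day.

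**Step 5. Comparison within the SAP.** ECG and biopsy are both performed at Visit 7 (EOT), but only the ECG shift table names the early discontinuation visit. With that endpoint for biopsies, all 84 days would be covered instead of 14.

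**Ultrasound.** SAP 7.10.7.1 has no table restricted to Week 12. It summarises post-baseline visits, so only the mapping in Steps 2 to 4 applies to it.

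**The case against.** The strongest reply is that little would be lost and nothing hidden. No biopsy is scheduled before Visit 7, so a finding before Day 71 needs a for-cause test or a biopsy taken because the woman was already leaving. In women who complete, abnormal histology would ordinarily be found at Week 12 and counted. Clinically significant abnormalities are recorded as adverse events (Protocol 8.8) and reach the treatment-emergent tables, which do not depend on Table 5. Disposition shows reasons for discontinuation, and all early-discontinuation and unscheduled data are listed. This stands, and it limits the consequence to the endometrial tables. It does not supply a complete summary of the named endpoint.

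A second reply is that Week 12 may be meant as Visit 7, which includes early termination. That is a possible intention, but SAP 5.4.6 maps by day and exempts only diary data. The SAP's Section 11 list of outputs is not in the text available, so the table specification cannot be checked.

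A reader might infer that the rule singles out women withdrawn for endometrial findings, or that the plan conceals harm. The documents do not support this. Everyone who terminates before Day 71 is omitted, whatever the reason; termination from Day 71 stays in Week 12; and withdrawal for an endometrial finding is on the Investigator's judgement. A reader might also assume a dropout rate and quote a zero-event upper bound for the smaller sample. The rate would be invented, and such a bound measures precision rather than the cases omitted.

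**Conclusion.** The point holds as a gap in tabulation. Read as written, the SAP leaves out of the biopsy shift table every early-termination biopsy before Day 71 and every unscheduled biopsy. It also loses from the by-visit table the unscheduled ones, those on Days 1–6, and those where a scheduled visit is closer to the nominal day. Women withdrawn before Day 71 for an endometrial finding are among those omitted, so the tabulated incidence can be incomplete and too low.

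The size is known only in days: 70 of 84 for the shift table. Of those 70, 29 to 38 days (6 + 23 to 6 + 32) are also lost from the by-visit table if whole visits are selected and the scheduled visits fall as in Steps 2 and 3. Days are not women, and 83% is not a share of subjects. The number of women affected would require the rate and timing of early termination, the share with a uterus and the frequency of abnormal findings, none of which the documents give.

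**What to change.** Amend SAP 7.10.7.2 before unblinding:

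- Run the biopsy shift table from baseline to the EOT/early discontinuation visit, using the SAP's own ECG wording.
- Add a per-arm incidence of abnormal histology among women with any post-baseline biopsy, based on the worst post-baseline adjudicated reading and including early-termination and unscheduled biopsies. Using the worst reading rather than the last prevents a later normal result from replacing an abnormal one.
- Report separately any biopsy without an adjudicated reading. Protocol 4.5.2 says only that reports or slides of on-study biopsies may be requested centrally, so some may lack one.
- In SAP 7.10.7.1, add an EOT/early discontinuation row to the ultrasound tables.

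The cost is SAP wording and one extra derived record. The downside is that exposure time at assessment varies somewhat between women; showing the study day of the biopsy beside the result would make that visible. Trial conduct does not change.

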### 7.10.8 Other Safety Assessments

Total score of PHQ-8 and total score of GAD7 will be summarized descriptively in tables by treatment and scheduled visit. (Table 14.3.8, Table 14.3.9) The data listings will be generated.

### 7.11 Pharmacokinetics Assessment

These analyses will be performed on the PK population.

Changes to the procedures or events, which may impact the quality of the PK data will be considered significant protocol deviations or events. These changes will include any circumstances that will alter the evaluation of the PK. In the case of a significant protocol deviation or event, PK data collected during the affected visit will be flagged.

### 7.11.1 Listings, and Descriptive Statistics

Plasma MT-8554 data will be listed for each subject and scheduled visit and treatment period with the same precision as provided by the bioanalytical laboratory. PK blood sample collection times, most recent dosing times, as well as derived actual sampling time relative to the most recent dose will be provided in a listing. The actual sampling time relative to the most recent dose will be calculated in hours and rounded to 2 DP.

## 7.12 Statistical/Analytical issues

### 7.12.1 Adjustments of covariates

In the efficacy analysis, repeated measures ANCOVA model with an unstructured covariance structure or ANCOVA will be performed with baseline as a covariate in order to consider the impact of the baseline on the change in each variable. More details were described in each analysis.

### 7.12.2 Data Handling of Dropouts or Missing

Missing data will not be imputed in the summary at each time point. The missing data will not be imputed for efficacy analyses. For AE start and/or end date missing or partial missing, the AE will be treated as TEAE if it cannot be determined a non-TEAE.

### 7.12.3 Interim Analyses and Data Monitoring

The details are described in Section 3.2 Interim Analysis.

### 7.12.4 Multiple Comparison/Multiplicity

In order to deal with multi-endpoint multiplicity, the efficacy analyses of primary and secondary endpoints will be conducted in the order fixed method. The details are described in Section 7.9 Efficacy Assessments.

The secondary analysis of primary variable and the analysis of other efficacy endpoints are performed from the exploratory perspectives and therefore no adjustment will be made for the multiplicity among variables and time points.

### 7.12.5 Subgroup Analysis

For Co-Primary endpoints will be summarized by treatment group for the following subgroup, as subgroup analyses. (Table 14.2.2.3.1, Table 14.2.2.3.2)

- Age group (age < 65, age  $\geq$  65)
- Race (White, Black or African American, Asian, others)
- BMI (BMI <30, BMI  $\geq$ 30 kg/m^2)
- Menopause status (Natural, surgical)
- Average daily VMS frequency (<Medn,  $\geq$ Medn), where Medn = Median of VMS frequency of ITT at baseline

**8. CHANGES FROM THE PROTOCOL**

Subgroup analysis of antidepressant using (Y, N) will not be performed because there are not enough subjects with using antidepressant for the analysis.

Analysis for PP Population does not apply to secondary endpoints. These analyzes were considered to be excessive.

**9. VALIDATIONS**

The tables, figures and listings (TFLs) planned in this SAP will be produced by [REDACTED] using SAS software version 9.4 (or above). The TFLs will be quality checked by statistics team in MTDA and [REDACTED] using SAS software version 9.3 (or above). The TFLs will be approved by MTDA.

[REDACTED]

**10. PROGRAMMING AND DATA PRESENTATION CONVENTIONS**

Listings will be presented in treatment, subject, visit (where applicable) and date (where applicable) order. Listings will be produced (landscape in MS Word) using PROC REPORT in SAS monospace font and pitch 8.

Summary tabulations will be presented by treatment group (and overall if appropriate), scheduled visit order (if appropriate). Continuous data summaries will present (unless stated otherwise) number of observations, mean, standard deviation, median, minimum and maximum. Categorical data summaries will present the number of observations and the corresponding percentage.

